I, the Investigator of Record, agree to conduct this study in full accordance with the provisions of this protocol. I will comply with all requirements regarding the obligations of investigators as outlined in the Statement of Investigator (Form FDA 1572), which I have also signed. I agree to maintain all study documentation for at least two years following the date of marketing approval for the study product for the indication in which it was studied. If no marketing application is filed, or if the application is not approved, the records will be retained for two years after the investigation is discontinued and the US Food and Drug Administration is notified. Publication of the results of this study will be governed by MTN policies. Any presentation, abstract, or manuscript will be made available by the investigators to the MTN Manuscript Review Committee, DAIDS, and the Population Council for review prior to submission.

I have read and understand the information in this protocol and will ensure that all associates, colleagues, and employees assisting in the conduct of the study are informed about the obligations incurred by their contribution to the study.

Name of Site Investigator

Signature of Site Investigator

Date

MTN-005

Expanded Safety and Adherence Study of a Non-medicated Intravaginal Ring

PROTOCOL SUMMARY

- Short Title:** Safety and Adherence of a Non-medicated Intravaginal Ring (IVR)
- Protocol Chair:** [name]
- Sample Size:** Total: 252 (168 and 84 in the IVR and No IVR arms, respectively)
India: 150 (100 and 50 in the IVR and No IVR arms, respectively)
US: 102 (68 and 34 in the IVR and No IVR arms, respectively)
- Study Population:** Sexually active, HIV-uninfected women between the ages of 18 and 45 years
- Sites:** Bronx-Lebanon Hospital Center, Bronx, NY, USA
National AIDS Research Institute, Pune, India
University of Alabama at Birmingham, Birmingham, AL, USA
- Study Design:** Multi-site, open-label, two-arm, randomized controlled trial comparing study IVR to no IVR with randomization of 2:1 (IVR: No IVR)
- Study Duration:** 16 weeks for each participant; 14 months approximate total study duration
- Study Regimen:** Participants will be randomized to study IVR or no IVR. The study IVR will be used for a 12-week period. Participants will be followed every 4 weeks until the 16-Week/Study Termination Visit

Table 1: Study Regimen

	Screening	Enrollment	4-Week	8-Week	12-Week	16-Week
GROUP	↓	↓	↓	↓	↓	↓
A		[STUDY IVR USE PERIOD]		TERMINATION
B		[NO IVR (SAME STUDY VISITS AS GROUP A)]				

Study Objectives

Primary Objectives

- Evaluate the safety of the study IVR in HIV-uninfected women over 12 weeks of use
- Evaluate the adherence to the study IVR in HIV-uninfected women over 12 weeks of use

Primary Endpoints:

- Evidence of Grade 2 or higher genitourinary events as defined by the Division of AIDS (DAIDS) Table for Grading the Severity of Adult and Pediatric Adverse Events, Version 1.0, Dec 2004 (Clarification dated August 2009), Addendum 1 (Female Genital Grading Table for Use in Microbicide Studies)
- For women randomized to the study IVR arm, participant report of frequency of study IVR removal (voluntary and involuntary) and duration without IVR inserted in vagina over 12 weeks of use

Secondary Objectives

- Describe changes in sexual behavior and changes in vaginal hygiene practices in the study IVR vs. no IVR group over 12 weeks of use/non-use
- Evaluate the acceptability of the study IVR in HIV-uninfected women over 12 weeks of use
- Measure vaginal flora characteristics, and descriptively examine changes in these characteristics over the course of study IVR use

Secondary Endpoints

- Per participant report, changes in sexual behavior and vaginal hygiene practices
- For women randomized to the study IVR arm, participant report of acceptability including genitourinary discomfort, ring insertion/removal issues, expulsions (including context of expulsion), and changes in participant and/or partner sexual feeling
- Changes in vaginal flora from enrollment to week 12 as measured by Gram stain Nugent score and quantitative culture (note that these quantitative vaginal cultures will only be available from the US sites, therefore reducing the available sample size for this objective)

Exploratory Objective

- Test candidate biomarkers in the cervicovaginal environment before and after the use of study IVR
- Evaluate the study IVR after 12 weeks of use for the presence of biofilms (US sites only)

Exploratory Endpoint

- Changes in vaginal biomarkers (US sites only)
- Presence of biofilms on study IVR surface (US sites only)

KEY ROLES

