2.5 Clinical Studies

2.5.1 Progering[®]

Progering[®] is a silicone elastomer progesterone-releasing ring; a non-medicated version of this ring will be studied in MTN-005.

Sivin and colleagues²⁸ compared the efficacy of Progering[®] to the T-Cu IUD among lactating women across nine clinics in Asia, Latin America, North Africa, and the US. Participants chose either the PVR (n=802) or the Copper T 380 A (T-Cu) intrauterine device (IUD, n=734). Women in this study inserted the PVR 4-9 weeks postpartum and were asked to replace the ring every three months, and continue use up to one year or until weaning. Follow-up visits were conducted at 1, 3, 6, 9, and 12 months and once again at two months following PVR discontinuation. Participants in the PVR group reported problems with expulsion and unexpected bleeding during the first month of PVR use. Importantly, Progering[®] use was not associated with macroscopic lesions, although the majority of participants reported discharge, leukorrhea, or vaginitis. Overall, Progering[®] was found to be a well-accepted method of contraception during lactation.

The safety and efficacy study that ultimately led to the registration of the PVR in Chile was conducted by Massai et al., among 547 lactating women at three different clinics.¹⁴ Participants chose either the PVR (n=285) or the T-Cu IUD (n=262). Women inserted the PVR 5-9 weeks postpartum. Women in the PVR arm were asked to use a PVR for three months at a time for either one year or until weaning, whichever came first. Follow-up visits were conducted every three months. Colposcopic examinations were conducted in 45 participants using the PVR and 280 participants were included in the PVR safety analysis. Changes to the vaginal epithelium were found in 8 participants. Two participants presented with vaginal abrasion (one required no follow-up and the other resolved after three months), and the remaining 6 presented with minor changes. No serious adverse events (SAE) were found in women using the PVR. Results from this study were used as the reference group for the study below.

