7.2 Enrollment Visit

Table 5: Enrollment Visit

Enrollment Visit	
Component	Procedures
Administrative and Regulatory	
 • Review/update locator information • Obtain written informed consent for enrollment and storage and future testing of specimens • Confirm eligibility • Provide available test results • Follow procedures for randomization assignment • Schedule next study visit, if applicable • Provide reimbursement for visit

Behavioral		
 • Administer baseline behavioral assessment • Administer baseline acceptability assessment • Provide counseling 
 ○ Contraceptive ○ HIV/STI risk reduction/male condom ○ Protocol adherence ○ For Group A, product use/adherence ○ HIV testing process*
Clinical		
 • Update obstetric history • Update medical/menstrual history • Update concomitant medications • Document pre-existing conditions • Perform targeted physical exam (see Appendix III) • Collect urine sample • Collect blood sample • Perform pelvic exam (see Appendix III) • Perform naked eye examination and colposcopic examination as described by the CONRAD/WHO Manual for the Standardization of Colposcopy for the Evaluation of Vaginal Products (Update 2004) to assess condition of vaginal and/or cervical epithelium or blood vessels. Digital images may be recorded • Collect pelvic samples • Treat or prescribe treatment for symptomatic UTI/RTIs/STIs or refer for other findings*
Laboratory	Urine	
 • Qualitative hCG • Dipstick UA* • Urine culture*
	Blood	
 • Plasma archive • Syphilis serology* • HIV-1 test*
	Pelvic Samples	
 • Gram stained smear of vaginal fluid, obtained from lateral vaginal wall • Vaginal swabs for vaginal flora assessment • Cervical swab for innate factors (US sites only) • Vaginal fluid tested for Trichomonas vaginalis by rapid test (CLIA waived test)* † • Vaginal pH* † • Vaginal fluid for wet mount microscopy (KOH for vulvovaginal candidiasis)* † • Vaginal fluid for wet mount microscopy (saline for BV)* † • Herpes culture †* • Cervical swab for NAAT for GC/CT*

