7.3 Follow-up Visits

All follow-up visits should be scheduled, ideally, on dates (within the ± 7 day visit window) when the participant is not on her menses. If a study visit does occur during the participant's menses, all visit procedures (except pelvic exam/colposcopy and associated pelvic lab specimens) should be performed at that time. If indicated, the pelvic exam, colposcopy, and associated specimen collections required for the given visit will be rescheduled for a date as soon as practical (preferably within the ± 7 day visit window) after the end of participant's menses.

Table 6: Follow-up Visits

Follow-up Visits: 4-Week, 8-Week, and 12-Week Visits		
Component		Procedures
Administrative and Regulatory		
 • Review/update locator information • Provide available test results • Schedule next study visit • Provide reimbursement for visit
Behavioral		
 • Administer follow-up behavioral assessment • Administer follow-up adherence assessment (Group A only) • Administer final acceptability assessment (for Group A participants at 12-Week Visit) • Provide counseling 
 ○ Contraceptive ○ HIV/STI risk reduction/male condom ○ Protocol adherence ○ For Group A, product use/adherence (4-and 8-Week Visit Only) ○ HIV testing process*
Clinical		
 • Update medical/menstrual history • Review/update concomitant medications • Perform targeted physical exam (see Appendix III) • Collect urine sample* • Collect blood sample* • Perform pelvic exam (see Appendix III) • Perform naked eye examination (all study visits) and colposcopic examination (12-Week Visit only, and if indicated at 4-and 8-Week Visits) as described by the CONRAD/WHO Manual for the Standardization of Colposcopy for the Evaluation of Vaginal Products (Update 2004) to assess (1) condition of vaginal and/or cervical epithelium or blood vessels and (2) quantity and quality of vaginal discharge. Digital images of abnormal findings may be recorded • Collect pelvic samples • Treat or prescribe treatment for symptomatic UTI/RTIs/STIs or refer for other findings*
Laboratory	Urine	
 • Qualitative hCG* • Dipstick UA* • Urine culture*
	Blood	
 • Syphilis serology* • HIV-1 test*

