	Pelvic Samples	
 • Gram stained smear of vaginal fluid, obtained from lateral vaginal wall • Vaginal swabs for vaginal flora assessments • Vaginal fluid tested for Trichomonas vaginalis by rapid test (CLIA waived test)* † • Vaginal pH* † • Vaginal fluid for wet mount microscopy (KOH for vulvovaginal candidiasis)* † • Vaginal fluid for wet mount microscopy (saline for BV)* † • Herpes culture †* • Cervical swab for NAAT for GC/CT* • US sites only: a biofilm assessment will be performed on the used ring that is removed at the 12-Week Visit if the ring is removed by a study clinician. 
 ○ In the event that an IVR is removed at an earlier visit, the used ring will have a biofilm assessment if assessment criteria are met, including IVR removal by a study clinician/designee.
Study Product Supply		
 • Provide study specified male condoms • Study clinician/designee to remove used study IVR at 12-Week Visit • Provide study IVR at 4-and 8-Week Visits in case of ring removal/expulsion* • Collect used study IVR at 4-and 8-Week Visits in case of ring removal/expulsion* 
 ○ In case of ring expulsion or removal, participants may also receive a bottle of water with which to rinse the study ring (4- and 8-Week Visits only)

*If clinically indicated

† Per local standards/guidelines

7.4 16-Week/Study Termination Visit

Table 7: 16-Week/Study Termination Visit

16-Week/Study Termination Visit	
Component	Procedures
Administrative and Regulatory	
 • Review/update locator information • Provide available test results • Provide reimbursement for visit • Schedule next study visit, if applicable
Behavioral	
 • Administer final behavioral assessment (in the event that a participant drops out of the study prior to the 16-Week Visit, the final behavioral assessment will not be administered) • Provide counseling 
 ○ Contraceptive ○ HIV testing process ○ HIV/STI risk reduction/male condom • Administer final acceptability assessment (for Group A in the event that use of the study IVR is permanently discontinued at an earlier visit)*

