7.8 Adherence, Acceptability and Behavioral Change

7.8.1 Adherence

For participants in Group A, adherence will be measured at the 4-, 8- and 12-Week Visits. Adherence will be measured via several participant self-report strategies. The questions will assess the frequency of study IVR use for established periods prior to the

scheduled follow-up visits. A series of questions will ask whether the study IVR was out, whether it was removed or expelled, under what conditions it was removed or expelled, and whether it was re-inserted. Additional questions will assess sexual activity, as well as condom and study IVR use during sex. A combination of interviewer-administered questionnaires and ACASI will be employed to capture the above information. Study staff will provide participants with guidance on strategies to optimize recall of relevant behavioral and adherence data.

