10.4.3 Acceptability Endpoints

Several components of acceptability (e.g., report of discomfort, removal and insertion difficulties, episode of expulsions, bowel, urinary and sexual difficulties (see Section

7.8)) will be used to assess overall acceptability. Each component will be assessed by a dichotomous measure where women will be categorized into (1) those reporting no acceptability issues during the 12 weeks of study IVR use (e.g., those reporting no discomfort) and (2) those reporting at least one issue during the 12 weeks of study IVR use (e.g., those reporting some discomfort). Acceptability can only be assessed among the 168 women randomized to the study IVR arm. An acceptability endpoint is defined as a negative report by a participant, on any of the above components of acceptability. A sample size of 168 women will provide a precision of 6.4% (i.e. half-width of the 95% exact confidence interval) assuming an observed acceptability of 80%. Substantial heterogeneities in acceptability between the Indian and the US sites might be observed in which case acceptability will be estimated separately for Indian and US women. For the Indian site, a sample size of 100 women using the study IVR will provide a precision of 8.3% assuming an observed acceptability of 80% while this precision would be 10.2% with a sample size of 68 US women using the study IVR. Due to the smaller sample size within each site, no formal comparison will be performed for comparing adherence and acceptability between sites.

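### Acceptability is scored over 12 weeks of ring use, but discomfort, insertion/removal and sexual-feeling items are asked on ring only once, at Week 12

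*Protocol*

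**What the plan says.** **Endpoint.** The Protocol Summary and section 10.2.2 define acceptability, in the ring arm only, as "participant report of acceptability including genitourinary discomfort, ring insertion/removal issues, expulsions (including context of expulsion") together with changes in the woman's or her partner's sexual feeling.

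**Window.** Section 10.4.3 makes each component dichotomous. It separates "those reporting no acceptability issues during the 12 weeks of study IVR use" from "those reporting at least one issue during the 12 weeks of study IVR use". A negative report on any component counts. Section 10.8.3 analyses the proportion of women with one or more negative reports in follow-up, with a 95% confidence interval.

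**Schedule of the acceptability questionnaire.**
- Enrollment (Table 5): "Administer baseline acceptability assessment". This is before any on-study ring use.
- Weeks 4 and 8: none. The cells in the acceptability row of Appendix I are blank.
- Week 12 (Table 6): "Administer final acceptability assessment (for Group A participants at 12-Week Visit").
- Week 16 (Table 7), for women who stopped early: "Administer final acceptability assessment (for Group A in the event that use of the study IVR is permanently discontinued at an earlier visit").

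**What is asked every 4 weeks.** Section 7.8.1 gives Group A an adherence assessment at Weeks 4, 8 and 12. It asks whether the ring was out, "whether it was removed or expelled, under what conditions it was removed or expelled, and whether it was re-inserted". Section 8.3.1 records adverse events of any grade from randomization to termination.

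**Acceptability items.** Section 7.8.2 lists ease of insertion and removal, feeling the ring, partner awareness and attitude, and future willingness. Expulsion is not in that list.

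**The concern.** The endpoint asks whether an issue ever occurred in 12 weeks, but the questionnaire written for it is given once, at the end. A woman who found insertion awkward, felt the ring, or noticed a change during sex in the first weeks and then adapted must remember this and report it at Week 12. With an any-issue endpoint, a forgotten issue moves a woman from the issue group to the no-issue group, never the other way. The resulting error therefore favours the ring.

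Elsewhere the protocol uses short recall. Adherence is asked every 4 weeks with guidance to help recall (7.8.1), and several behaviour items use 7-day or one-month windows (10.4.5). Section 2.5.1 also compares two studies of the parent ring, one with visits every three months and one with monthly visits. It reports 12.4 and 32.3 events per 100 women-months (32.3 / 12.4 = 2.6) and attributes the higher rate to visit frequency. That comparison is not randomised, the rings were used for different lengths of time, and it concerns events rather than acceptability items. It supports the direction only.

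At stake is a secondary proportion in the ring arm, on a question where section 2.7.2 says data are lacking.

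**Working it through.** **Step 1: which components rest on the single recall.**

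| Component | Asked at Weeks 4 and 8? | Asked at Week 12? |
|---|---|---|
| Expulsion, removal and their context | Yes, adherence assessment (7.8.1) | Yes |
| Discomfort, feeling the ring | No structured item; may surface as an adverse event (8.3.1) | Yes |
| Ease of insertion and removal | No | Yes |
| Sexual feeling, hers or her partner's | No; 7.8.1 asks about sexual activity and about condom and ring use during sex | Yes |

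The single recall therefore affects the last three rows, not the first.

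**Step 2: the plan's own precision.** Section 10.4.3 gives half-widths of 6.4% (n = 168), 8.3% (n = 100) and 10.2% (n = 68) at 80% acceptability. For the exact (Clopper-Pearson) 95% interval, the lower limit is the 0.025 quantile of Beta(x, n − x + 1), the upper limit is the 0.975 quantile of Beta(x + 1, n − x), and the half-width is (upper − lower)/2.
- 134/168: (0.8556 − 0.7288)/2 = 6.34 points
- 80/100: (0.8733 − 0.7082)/2 = 8.26 points
- 54/68: (0.8826 − 0.6788)/2 = 10.19 points

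The stated figures reproduce to within 0.1 point.

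**Step 3: size of the recall loss.** Let
- p = true proportion with an issue: 0.20, from the plan's 80% acceptability;
- f = share of those women whose issues were all early: assumed 0.25 to 0.75;
- r = probability that such a woman reports the issue at Week 12: assumed 0.5 to 0.9.

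Observed issue rate = p(1 − f) + p·f·r, so the overstatement of acceptability = p·f·(1 − r).

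Overstatement in percentage points at p = 0.20:

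| f | r = 0.9 | r = 0.7 | r = 0.5 |
|---|---|---|---|
| 0.25 | 0.5 | 1.5 | 2.5 |
| 0.50 | 1.0 | 3.0 | 5.0 |
| 0.75 | 1.5 | 4.5 | 7.5 |

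For example, 0.20 × 0.75 × (1 − 0.5) = 0.075, so observed acceptability would be 87.5%. To exceed the 6.4-point half-width at p = 0.20, f·(1 − r) must exceed 0.064/0.20 = 0.32. Only one of the nine cells does so (0.75 × 0.5 = 0.375).

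The loss scales with p. At p = 0.40 the range doubles, to 1 to 15 points. It is zero if recall is complete. The model applies the loss to every issue, so it overstates the effect to the extent that Week 4 and 8 expulsion reports count.

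**The case against.** A reader might draw four stronger conclusions. The documents support none of them.

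- **That every component is asked only once.** Expulsion, removal and their context are asked at Weeks 4, 8 and 12. Discomfort can also be recorded as an adverse event of any grade.
- **That the Week 4 and 8 reports are excluded from the endpoint.** Section 10.4.3 refers to the whole of section 7.8, which includes the adherence questions, and 10.8.3 counts negative reports over follow-up. Pooling across visits fits this wording. The text leaves the matter open, and naming the source forms is a detail that an analysis plan could supply.
- **That the parent ring's data show early problems of the kind asked only once.** Section 2.5.1 says "Participants in the PVR group reported problems with expulsion and unexpected bleeding during the first month of PVR use". Expulsion is already asked every 4 weeks, and bleeding is not a listed acceptability component. The women were lactating users of a progesterone ring. Nothing cited shows that discomfort, insertion difficulty or sexual-feeling problems cluster in the first month.
- **That acceptability is known to be overstated by a given amount.** No document gives the share of early issues or the recall rate. Persistent or recurrent problems would still be current at Week 12.

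It is also fair to say that this is a secondary, single-arm estimate with no threshold or test, and that an end-of-use assessment suits summary items such as future willingness. These points limit the importance of the concern. They do not remove it: no short-recall structured question covers three of the component groups, and an analysis plan cannot recover answers to questions that were never asked.

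**Conclusion.** The point holds for the items outside the 4-weekly adherence assessment: discomfort or feeling the ring, ease of insertion and removal, and sexual feeling. For continuing users these rest on one recall of up to 12 weeks, although the endpoint covers the whole ring period. Omission can only lower the count of women with an issue, so the tendency is to overstate acceptability.

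The size is not known. At 80% true acceptability, with assumed early-issue shares of 25-75% and recall of 50-90%, it is 0.5 to 7.5 points. Most of that range lies inside the 6.4-point half-width, and only the least favourable combination exceeds it. Unlike sampling error, however, it has a direction and would not shrink with more women. This is a cheap improvement to a secondary endpoint. It does not threaten the trial's primary conclusions.

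**What to change.** 1. In Table 6 and Appendix I, add the short discomfort, insertion/removal and sexual-feeling items to the questionnaires that Group A already completes at Weeks 4 and 8. Keep the full questionnaire, including future willingness, at Week 12.
2. In 10.4.3 and 10.8.3, state that a participant-reported issue at Week 4, 8 or 12 counts toward the endpoint, including expulsions from the adherence assessment.
3. Show discomfort recorded only as an adverse event in a supporting analysis. The endpoint is participant report, whereas adverse events include findings observed by staff, so merging them would change the endpoint.

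**Cost.** A few extra questions at two existing visits and some wording, with no new visits. Questionnaires become slightly longer, and the acceptability figure will probably be somewhat lower.
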